6.0 Recruitment Methods

Recruitment will begin once IRB approval has been received and will occur through BostonSight. The subject pool will consist of patients who are actively coming through the clinic. We anticipate that all our subjects will be from the current patient population at BostonSight. Patients will be recruited via our website, mailing and/or email and at office visits. If a patient is interested in participating in the study, they will be directed to the principal investigator or the study coordinator who will go over the study and ask the screening questions. If they are eligible based on the screening criteria, they will be invited for participation in the study. If the person calls to learn about the study, the investigator or coordinator will use the outline to determine initial eligibility. Current patients of BostonSight may also be recruited as a result of a search of the patient database.

7.0 Multi-Site Research Communication – N/A

8.0 Study Timelines

It is anticipated that to enroll all study subjects, it will take approximately 3 months. The estimated date for completion of this study is 6 months after the start of recruitment.

The total duration of the subjects' participation in the study will be approximately 1-2 months (to complete all 3-4 visits). The visits include:

- Initial screening visit/baseline evaluation at BostonSight
- Scanning visit at EYEdeal Scanning, LLC (Needham, MA)
- One additional follow up scanning visit at EYEdeal Scanning, LLC (as necessary)
- Lens fitting evaluation visit

Study Visits:

TITLE: Pilot study to investigate the feasibility, reliability, and efficiency of utilizing ocular surface optical coherence tomography to automate PROSE fitting

PROTOCOL NUMBER: BFS OCT-01

IRB APPROVED

Jul 14, 2020

NCT04649177

Initial Visit at BostonSight (present wearing PROSE device for at least 45 minutes)

Pre-visit calls:

- COVID-19 screening and travel forms:
 - Contact subject one week before visit to complete COVID-19 travel form
 - Contact subject one day before visit to complete COVID-19 screening form

Visit 1:

- Complete Informed Consent
- Complete patient screening checklist
- Complete medical and ocular history intake
- Document information about current PROSE device in the study eye
 - Current PROSE device parameters
 - Number of cuts needed to dispense initial standard PROSE lens in study eye (chart review)
- Current PROSE device performance questionnaire (0-10 scale)
 - Awareness
 - Comfort
- Check current VA with PROSE (logMAR, Appendix D)
- PROSE fit evaluation
 - Slit Lamp Biomicroscopy evaluation of current PROSE device fit in study eye
 - Confirm acceptable fit, no further customizations, replacement or retreatment required at this time (inclusion criteria requirement)
- Baseline Slit Lamp Biomicroscopy without PROSE device or any contact lens applied in the study eye

EYEdal Scanning, LLC Visit(s) (Needham, MA) (within 4 weeks of Initial BostonSight Visit, no lens for 3 days prior to visit):

Pre-visit calls:

- Contact subject one week before visit to complete COVID-19 travel form
- Contact subject 4 days before visit to remind them not to wear lenses for the next three days.
- Contact subject one day before visit to complete COVID-19 screening form

TITLE: Pilot study to investigate the feasibility, reliability, and efficiency of utilizing ocular surface optical coherence tomography to automate PROSE fitting

PROTOCOL NUMBER: BFS OCT-01

IRB APPROVED

Jul 14, 2020

NCT04649177

Visit 2/3:

Visit Location and Subject Preparation

This visit for the scanning of the ocular surface will take place at EYEdeal, Scanning, LLC ([name]) under the oversight of [name] and under an additional IRB approved protocol and consent (submitted separately by [name]).

The measurements taken with the “EYEdeal Scanning ophthalmic instrument” are performed non-mydriatic (pupil dilation drops will not be administered). Scanning tomography measurements will be performed at the EYEdeal Scanning facility by an EYEdeal engineer, with the assistance of a licensed optometrist or ophthalmologist from BostonSight who will carefully expose the ocular surface by holding the eyelids open in a suitable position for scan acquisition. The EYEdeal Engineer will be in charge of and completely controlling all aspects of the “EYEdeal Scanning Ophthalmic Instrument”. The EYEdeal engineer will have no contact and will not perform any examination or procedure on the patient. The licensed BostonSight optometrist or ophthalmologist will have no interaction and no control of the “EYEdeal Scanning Ophthalmic Instrument”. The licensed BostonSight optometrist will interact with the patient and perform the eyelid maneuvers as described above.

Methodology

The volunteer will be asked to look into a 25 mm half silvered alignment mirror located in the center of the scanning instrument. A stationary TV camera located behind the partially transmissive alignment mirror monitors eye position throughout the scan. A fixation target may also be added to the instrument. A resting mechanism is provided to both support the head and place the eye within the measurement range of the instrument. At no time is the instrument closer than 76mm (3 inches) to the surface of the eye. The initial alignment will be performed using the alignment TV camera such that the eye pupil is imaged in the center of the camera picture. The scanning beams will be directed toward the eye as the volunteer is instructed to keep looking at the reflection of their eye in the alignment mirror and or the fixation target. Once the subject is aligned, the licensed optometrist or ophthalmologist will hold the lids open with their fingers or cotton tipped applicators for adequate exposure and the scan of the central cornea and scleral region is recorded. This lid holding procedure is routinely used by doctors in an ophthalmic office during eye examinations. The laser scan will last about 2-3 seconds and might need to be repeated due to eye motion, exposure, blinks, or saccades during the scan. This visit will last a maximum of one hour or maximum of 10 scans on the study eye, whichever occurs first.

Data Collection and Security

Data to be collected in the investigation includes eye images and videos, and electronic data files containing various representations of eye topography. Subject identity cannot be directly determined from any of the images or videos. Subject confidentiality is assured with

TITLE: Pilot study to investigate the feasibility, reliability, and efficiency of utilizing ocular surface optical coherence tomography to automate PROSE fitting

PROTOCOL NUMBER: BFS OCT-01

IRB APPROVED

Jul 14, 2020

NCT04649177

procedures and protections in place at EYEdeal Scanning. Images, video, and data collected on the subjects are maintained on a single computer according to subject identification numbers. The randomly-chosen identification numbers are assigned during the first subject visit and will be stored separately from all other data. The identification numbers can only be linked to the subject via a single password-protected encrypted data file maintained by the PI. Password protected de-identified scan data will be provided to BostonSight on a flash drive or via email.

Data Analysis

The laser scan will produce a series of eye surface height data along each scanned meridian. This data will be processed by an algorithm to determine the shape of the measured meridian. All meridians will then be stitched together to generate a large area topography map and image of the eye. If the data is deemed inadequate or unreliable scans are obtained or optimal scans are not achieved within 1 hour, or if in excess of 10 scans are required, the subject may return on a future date for one additional visit to EYEdeal Scanning, LLC with the same time and scan number constraints.

BostonSight Fitting Visit (no lens for 3 days prior to visit)

Pre-visit calls:

- Contact subject one week before visit to complete COVID-19 travel form
- Contact subject 4 days before visit to remind them not to wear lenses for the next three days.
- Contact subject one day before visit to complete COVID-19 screening form

Visit 4:

- Update medical and ocular history
- Baseline Slit Lamp Biomicroscopy without PROSE device or any contact lens applied in the study eye
- Image-guided PROSE* fit evaluation
 - Slit Lamp Biomicroscopy evaluation of image-guided PROSE device fit in study eye.
 - BCVA (over-refraction as needed) – prescription will be based on current optimized standard PROSE lens
- PROSE device performance questionnaire (after 45 minutes of wear, if able/tolerable)
 - Awareness
 - Comfort
- Post 45 minutes wear time evaluation:

TITLE: Pilot study to investigate the feasibility, reliability, and efficiency of utilizing ocular surface optical coherence tomography to automate PROSE fitting

PROTOCOL NUMBER: BFS OCT-01

IRB APPROVED

Jul 14, 2020

NCT04649177

- Slit Lamp Biomicroscopy evaluation of image-guided PROSE device fit
- Optical Coherence Tomography imaging of central corneal clearance
- iTRACE imaging of lens rotation and decentration
- Clinician determination if image-guided initial fit could be dispensed after initial fitting visit

**Note: all manufactured PROSE devices will use standard materials and coatings. Lens material and Hydra-PEG coating will match patient's current habitual standard lens.*

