2.0 Background

Scleral lenses are contact lenses manufactured from a rigid gas permeable material (fluorosilicone acrylates) which are prescribed for several indications, including:

- improve best corrected visual acuity, such as for patients with ectasia or other corneal irregularities¹
- provide comfort, such as to address pain and photophobia associated with ocular surface disease
- support the health of the ocular surface to address acute and chronic ocular surface breakdown secondary to disease processes such as Dry Eye Syndrome, Stevens-Johnson Syndrome, Sjogren's Syndrome, Rheumatoid Arthritis, and Graft Versus Host Disease.²

The PROSE device is similar to a scleral lens in theory though it allows for unique customizations of the fit that are unavailable in currently commercially marketed scleral lens designs.

The fluid which fills a PROSE device serves as a liquid cushion between the back surface of the rigid gas permeable lens material and the front surface of the cornea. As such, a PROSE device serves as both a healing liquid bandage lens and as a refractive lens for improving vision by masking corneal irregularities.

PROSE device manufacture and customization is currently an iterative time-intensive process often requiring at least 5-10 office visits and trials of multiple prosthetic devices that incrementally approach the final, dispensed design.

TITLE: Pilot study to investigate the feasibility, reliability, and efficiency of utilizing ocular surface optical coherence tomography to automate PROSE fitting

PROTOCOL NUMBER: BFS OCT-01

IRB APPROVED

Jul 14, 2020

NCT04649177

The entire PROSE device sits on the sclera, referred to as the lens bearing surface and vaults over the cornea. This bearing surface must properly match the topography of each patient's eye to achieve proper lens orientation, optical performance and patient comfort. Custom fitting is currently performed manually and is often a protracted process that requires multiple fitting sessions. Training for new practitioners is a long process.

Automated methods to measure the complete corneal and scleral topography would provide a valuable tool for both clinicians and PROSE device manufacturers.

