3.0 Inclusion and Exclusion Criteria

The participant will be eligible to participate if the following criteria apply:

1. Written Informed Consent has been obtained prior to any study-related procedures
2. Male or female, 18 years of age and older prior to the initial visit
3. Established wearer of PROSE in the study eye with an optimized fit in the opinion of the clinician
4. No medical need for a PROSE retreatment or replacement lens at the time of enrollment in the study eye, in the opinion of the clinician
5. Initial PROSE fitting was initiated and completed at BostonSight, Needham
6. Current PROSE device does not have channels or fenestrations

TITLE: Pilot study to investigate the feasibility, reliability, and efficiency of utilizing ocular surface optical coherence tomography to automate PROSE fitting

PROTOCOL NUMBER: BFS OCT-01

IRB APPROVED

Jul 14, 2020

NCT04649177

7. Currently wears a PROSE device in the study eye primarily for an irregular ocular surface /irregular cornea (including but not limited to Keratoconus, Pellucid Marginal Degeneration, Ectasia, Post-Penetrating Keratoplasty, Corneal Scar, Trauma) **AND/OR** ocular surface disease
8. Has the ability to NOT wear the current PROSE device in the study eye for 3 days prior to scan and 3 days prior to first fitting appointment in the opinion of the investigator and subject
9. In the opinion of the investigator, the subject has the ability to follow study instructions
10. In the opinion of the investigator, the subject has the ability to complete all study procedures and visits

The participant would **NOT** be eligible to participate if at least one of the following criteria is met:

1. Is currently participating in any other type of eye-related clinical or research study
2. Is pregnant or nursing as reported by the subject
3. Has a condition or is in a situation which, in the investigator's opinion, may put the subject at significant risk, may confound study outcomes, or may significantly interfere with the subject's participation in the study
4. Has had previous ocular surgery within the past 12 weeks
5. Intolerance to PROSE wear
6. Inability to maintain stable fixation and exposure for ocular surface imaging
7. Corneal touch by the posterior surface of the device in current PROSE device
8. Allergy to sodium fluorescein
9. Patient is an employee of BostonSight
10. Subject is currently incarcerated.

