10.0 Procedures Involved

Once a subject has been identified, the initial visit will be scheduled.

See Appendix A "**PROSE/EYEdeal ophthalmic scanning instrument: Schedule of Assessments**" which reviews the list of procedures during each visit and the length of time expected per procedure and per visit.

The testing descriptions are summarized in the table below:

Test	Description
General History and Medications	Participants will be asked questions about their general medical, ocular and medication use histories along with contact lens use history if applicable.
Lens Evaluation	The PROSE device fit will be evaluated via traditional methods utilizing a slit lamp microscope and standard fluorescein dye.
Visual Acuity	The participant's vision in each eye will be measured with a high contrast visual acuity chart. The participant will be asked to cover

TITLE: Pilot study to investigate the feasibility, reliability, and efficiency of utilizing ocular surface optical coherence tomography to automate PROSE fitting

PROTOCOL NUMBER: BFS OCT-01

IRB APPROVED

Jul 14, 2020

NCT04649177

	one eye and read the chart, and this procedure will be repeated for the other eye.
Slit-lamp Examination	The participant's front portion of each eye and PROSE devices will be examined with a lighted microscope. The participant will be asked to place his/her chin on the chinrest and place his/her forehead against the bar and look straight ahead. The instrument's light will be shined onto the eye to visualize the ocular surface for approximately 4 minutes per eye.
Sodium Fluorescein	Sodium fluorescein staining will be used to evaluate ocular surface damage indicated by cell damage or death.
EYEdeal Scanning Ophthalmic Instrument	The EYEdeal Scanning Ophthalmic Instrument is a non-invasive laser product (see 12.0 for more details). The participant will be asked to place his/her chin on the chinrest of the instrument. The forehead is placed against the bar and he/she will be asked to look straight ahead. The investigator will perform a scan of the eye to obtain data relating to the shape of the anterior surface of the eye. Data obtained from these scans at baseline can then be used to manufacture a customized image guided PROSE device.

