23.0 Data Management

Data will be stored in a study paper file at BostonSight. Electronic data will be stored on a password-protected computer in a locked office. All study data will remain at BostonSight for a minimum of 3 years following study completion. The principal investigator will be responsible for maintaining study data security and subject confidentiality, and the PI and the study coordinator will be responsible for receipt and transmission of the data. The investigative team and inspectors from regulatory agencies such as the US Food and Drug Administration will have access to the data if requested for study monitoring or an audit.

All collected data will be documented on study documents and analyzed for differences between baseline and test data. Hypothesis testing will be performed using statistical analyses including parametric or nonparametric comparisons (i.e., t-tests, signed-rank tests), analysis of variance, general linear models, correlation, or regression techniques.

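### Vision is recorded as worn at Visit 1 but only as best-corrected acuity at Visit 4, so the planned difference compares unlike measures (minor; net direction not settled)

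*Protocol*

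**What the plan says.** **Visit 1 (Protocol 8.0).** The subject arrives already in the current device ("present wearing PROSE device for at least 45 minutes"). The vision item is "Check current VA with PROSE (logMAR, Appendix D"). The visit list contains no over-refraction and no best-corrected measurement.

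**Visit 4 (Protocol 8.0).** The subject comes after three days without a lens. Under the fit evaluation of the image-guided device, the vision item is "BCVA (over-refraction as needed) – prescription will be based on current optimized standard PROSE lens". The line gives no scale. It stands above the questionnaire and the block of assessments made after 45 minutes of wear, and that block contains no acuity item.

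**Test description (Protocol 10.0).** One entry serves both visits: "The participant's vision in each eye will be measured with a high contrast visual acuity chart". It is silent on over-refraction.

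**Analysis (Protocol 23.0).** "All collected data will be documented on study documents and analyzed for differences between baseline and test data". The methods named include "parametric or nonparametric comparisons (i.e., t-tests, signed-rank tests").

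**Endpoints (Protocol 9.0).** The list covers fit (slit lamp, central clearance, iTRACE), whether the first image-guided device could be dispensed, and awareness and comfort scores. Visual acuity is not on it.

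**The concern.** A baseline-to-test difference means something only if the same quantity is measured both times. Here the baseline is acuity through the lens as worn, and the test value is acuity after the examiner may have added correction. Blur caused by the image-guided device can be removed before its value is written down. Blur through the current device stays in its value.

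If the as-worn acuity of the image-guided device is not recorded at Visit 4, no later analysis can recover it. The gap is therefore in data collection, and a statistical analysis plan could not close it. Acuity through the lens as made also bears on the study's practical question, namely whether a single scan-based device is good enough to dispense. Irregular cornea is one of the entry groups.

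**Working it through.** **1. The plan's own figures.** The Protocol gives no acuity difference, standard deviation or power, so there is no vision figure to reproduce. Its only sample-size figure is 12 recruited for 10 analysed with 10–20% drop-out. 10/(1 − 0.10) = 11.1, rounded up to 12, and 10/(1 − 0.20) = 12.5, rounded up to 13. That agrees with 12 to within one patient and does not affect this point.

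**2. The two visits side by side.**

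| | Visit 1, current device | Visit 4, image-guided device |
|---|---|---|
| Measure | acuity as worn | best-corrected acuity |
| Over-refraction | none listed | where needed |
| Scale | logMAR | not stated in the line |
| Wear beforehand | at least 45 minutes | none for 3 days; listed before the 45-minute block |

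**3. What the difference contains.** For one eye, on logMAR (lower is better), let C and T be as-worn acuity with the current and image-guided devices. Let h ≥ 0 and g ≥ 0 be what over-refraction would recover through each, and let w be the effect of the wear-time difference, of either sign.

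- Recorded difference: (T − g + w) − C.
- As-worn contrast, T − C: the error is −g + w.
- Best-corrected contrast, (T − g) − (C − h): the error is −h + w.

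Whichever contrast is wanted, the over-refraction term is zero or favours the image-guided device. It vanishes for the first contrast if g = 0 and for the second if h = 0. The sign of w is unknown, so the sign of the total is unknown too.

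**4. Size of the over-refraction term (all inputs assumed).** Mean shift = share of eyes that gain × gain per eye. With 10–50% of eyes gaining 0.05–0.20 logMAR, it runs from 0.10 × 0.05 = 0.005 to 0.50 × 0.20 = 0.10 logMAR.

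**5. Effect on a test.** Take two truly equal devices, w = 0, n = 10, a two-sided paired t-test at 0.05, and noncentrality = shift/SD × √10. The shift is treated as constant across eyes.

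| Mean shift | SD of differences | Noncentrality | Chance of a significant difference |
|---|---|---|---|
| 0 | any | 0 | 5% |
| 0.02 | 0.10 | 0.63 | 8.8% |
| 0.02 | 0.05 | 1.26 | 20.5% |
| 0.05 | 0.10 | 1.58 | 29.3% |
| 0.05 | 0.05 | 3.16 | 80.3% |

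**6. Masking of a loss (assumed).** If the image-guided device is L worse as made and over-refraction recovers a fraction r, the recorded loss is L(1 − r). For L = 0.1 to 0.2 logMAR this is 0.1 to 0.2 at r = 0, 0.05 to 0.10 at r = 0.5, and zero at r = 1.

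**The case against.** A reader might infer that the comparison is known to favour the image-guided device. The documents do not support that, for three reasons.

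- **Residual error is not shown.** Over-refraction is conditional, and subjects enter with a lens already judged good: "Established wearer of PROSE in the study eye with an optimized fit in the opinion of the clinician". That criterion concerns fit and requires no current refraction, so it makes residual error less likely without excluding it.
- **Wear time could act the other way.** Visit 4 acuity may be taken early in an unfamiliar lens after three days without one. Even this reading rests on the order of bullets, which the Protocol does not say is chronological.
- **The unseen appendices could bear on it.** Section 10.0 refers to Appendix A for the visit procedures, and the Visit 1 acuity item refers to Appendix D. Neither is shown.

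There is also a fair case for best-corrected acuity at Visit 4. The scan supplies shape and the prescription comes from the current lens, so over-refraction separates a power mismatch from optical quality. Section 2.0 itself gives the indication in those terms: "improve best corrected visual acuity, such as for patients with ectasia or other corneal irregularities". This justifies collecting the measure at Visit 4. It does not justify subtracting an as-worn baseline from it.

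Finally, vision is not a listed endpoint, and only the general sentence in Section 23.0 brings it into a comparison. That stands, and it limits the weight of the point.

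**Conclusion.** The point holds as a mismatch of measures. As written, the plan records as-worn acuity at one visit and only best-corrected acuity at the other, and commits to differencing all collected data. The over-refraction component runs one way, towards the image-guided device. The documents do not give its size, which may be zero. The wear-time component has unknown direction, so no net bias can be claimed.

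The 0.005 to 0.10 logMAR range, the test probabilities and the 0.1 to 0.2 logMAR loss are illustrations on assumed inputs, not estimates for this trial. Severity is minor: a supporting comparison is affected, and the endpoints listed in Section 9.0 are not.

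**What to change.** - **Visit 4.** Record logMAR acuity through the image-guided device alone, before any over-refraction and at a wear time matched to Visit 1 where tolerated. Then record the over-refraction and the best-corrected acuity.
- **Analysis.** Compare Visit 1 acuity only with the Visit 4 value taken without over-refraction. Report Visit 4 best-corrected acuity descriptively, unless the same over-refraction step is added at Visit 1. In that case, also compare best-corrected with best-corrected.
- **Check.** Make sure Appendices A and D describe the same sequence.

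**Cost.** A few minutes of chart reading and a worksheet change, with no extra visit or equipment. Adding the step at Visit 1 would take a little more examiner time. The acuity reported for the image-guided device may look slightly less favourable.

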5.0 Number of Subjects

A minimum of 10 current PROSE patients with a primary PROSE treatment indication of an irregular ocular surface/irregular cornea (including but not limited to Keratoconus, Pellucid Marginal Degeneration, Ectasia, Post-Penetrating Keratoplasty, Corneal Scar, Trauma) **AND/OR** ocular surface disease will be enrolled in the study. We can approximate a 10-20% drop-out rate, so we will expect to recruit 12 patients total. The first 10 patients to be eligible and complete the study will be used for data analysis.

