9.0 Study Endpoints

The primary endpoints in this study are as follows:

1. Fit evaluation of image-guided PROSE device
 - a) Overall fit parameters (slit lamp)
 - b) Central clearance ordered vs central clearance observed (slit lamp and OCT)
 - c) iTRACE (rotation and decentration)
2. Evaluate ability to dispense after manufacturing one PROSE device with image guided system (YES/NO)
3. PROSE device performance questionnaire (awareness and comfort both graded 0 to 10)

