15.0 Withdrawal of Subjects

Subjects will be withdrawn from the study if they are unable to complete the tasks in the study protocol. In addition, if they experience an adverse event in which the investigator does not feel that the subjects should continue, they will be withdrawn.

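### Visit 4 does not say whether a subject who removes the image-guided lens before 45 minutes is still scored for awareness and comfort, and the completer-only analysis set may replace that subject

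*Protocol*

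**What the plan says.** Section 9.0 of the protocol names three primary endpoints. Two matter here:

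- Endpoint 2: "Evaluate ability to dispense after manufacturing one PROSE device with image guided system (YES/NO").
- Endpoint 3: "PROSE device performance questionnaire (awareness and comfort both graded 0 to 10").

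In section 8.0, Visit 4 lists one administration of the questionnaire for the image-guided lens: "PROSE device performance questionnaire (after 45 minutes of wear, if able/tolerable"). The next item is "Post 45 minutes wear time evaluation", with slit lamp, OCT and iTRACE items below it. The last item of the visit is "Clinician determination if image-guided initial fit could be dispensed after initial fitting visit". Visit 4 gives no other time for the questionnaire and does not ask for minutes worn.

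Three further statements bear on who is analysed:

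- Section 5.0: "The first 10 patients to be eligible and complete the study will be used for data analysis".
- Section 15.0: "Subjects will be withdrawn from the study if they are unable to complete the tasks in the study protocol".
- Section 8.0 describes participation as the time needed "to complete all 3-4 visits".

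Completion of the study is not defined. Appendix A, the schedule of assessments, is not in the text at hand and may add detail.

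**The concern.** Failure to tolerate the new lens is itself an outcome of the lens under test. Section 3.0 admits only established wearers with an optimized habitual fit and excludes people intolerant of PROSE wear. Early removal at Visit 4 would therefore plausibly reflect the image-guided lens.

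If early removal means that the two questions are not asked, endpoint 3 is missing for the subjects with the worst experience, and the comparison with Visit 1 moves toward no difference. If the same subject is also treated as a non-completer, the clearest NO on endpoint 2 leaves the analysis and a later subject takes the place. Both effects favour the device.

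Missing-data methods can be left to a statistical analysis plan. The time of collection, the withdrawal rule and the analysis set, however, are all set in this protocol. No later plan can recover a score that was never asked for.

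**Working it through.** **Recruitment figure.** Section 5.0 gives a target of 10, drop-out of 10-20% and recruitment of 12. With n = 10/(1 - d), d = 10% gives 11.1, rounded up to 12, and d = 20% gives 12.5, rounded up to 13. The stated 12 is consistent with this, and no stated figure is wrong. It leaves up to two spare subjects.

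**Two readings of the text.**

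| Question | Stricter reading | Softer reading |
|---|---|---|
| Tolerance clause at Visit 4 | No questionnaire unless 45 minutes is reached | Only the wear time is relaxed; the questionnaire is still given |
| Completion (5.0, 8.0, 15.0) | An unfinished task means withdrawal and replacement | Attending Visit 4 completes the visits |
| Endpoint 3 | Score missing | Score present |
| Endpoint 2 | NO may be lost | NO counted |

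The visible text does not choose between the columns.

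**Endpoint 2, assumed illustration.** Inputs: 12 subjects fitted (the protocol plans 12 recruited), k of them intolerant, and every subject who tolerates the lens a YES. Intervals are exact (Clopper-Pearson). The lower limit is the 2.5% quantile of Beta(x, n - x + 1). The upper limit is the 97.5% quantile of Beta(x + 1, n - x), or 1 when x = n.

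| k | First 10 completers | All 12 fitted |
|---|---|---|
| 0 | 10/10 = 100% (69.2-100%) | 12/12 = 100% |
| 1 | 10/10 = 100% (69.2-100%) | 11/12 = 91.7% (61.5-99.8%) |
| 2 | 10/10 = 100% (69.2-100%) | 10/12 = 83.3% (51.6-97.9%) |

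If instead 8 of the 10 completers are a YES and k = 2, the contrast is 8/10 = 80% (44.4-97.5%) against 8/12 = 66.7% (34.9-90.1%).

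**Endpoint 3, assumed illustration.** Let k of 12 be unscored, each d points worse than at Visit 1 (d counted in the unfavourable direction, since the protocol does not state which end of the scale is good), and let the others average no change. The reported mean change is 0 whatever k is. The mean over all 12 is -(k × d)/12:

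- k = 1: d = 3 gives -3/12 = -0.25; d = 7 gives -7/12 = -0.58.
- k = 2: d = 3 gives -6/12 = -0.50; d = 7 gives -14/12 = -1.17.

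**How likely one such subject is.** The protocol gives no intolerance rate. For an assumed rate p, the chance of at least one among 12 is 1 - (1 - p)^12: 46% at p = 5%, 72% at 10% and 93% at 20%.

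**The case against.** The strongest reply is that the harm needs the less natural reading. The tolerance clause stands beside the wear time inside the same parenthesis, so it may well relax only the 45 minutes and leave the questionnaire in place. Because the protocol makes that wear time conditional, a subject who stops early has arguably followed it and has not failed a task under section 15.0. Visit 4 is the last visit, so attending it can count as completion. All of this is fair, and on that reading nothing is lost.

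A reader might also infer that the dispense decision requires 45 minutes of wear because it is listed after the post-wear evaluation. The documents do not support that. Neither section 8.0 nor section 9.0 attaches a wear-time condition to the YES/NO, the indentation of the list is lost in the text at hand, and NO is available for a lens that cannot be tolerated. Any loss from endpoint 2 would come from sections 5.0 and 15.0 together, not from the questionnaire line.

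The size is also open to challenge. The number intolerant, the score changes and the YES rate are all assumed. If drop-outs occur before Visit 4, fewer spare subjects remain to replace anyone. The intervals overlap widely.

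What stands is that the text does not say whether the questions are asked at early removal, and completion is undefined while the analysis set depends on it. Two examiners could act differently on a primary endpoint.

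**Conclusion.** The point holds as an ambiguity in what is collected and who is analysed, with a possible bias in favour of the device. It is not a demonstrated loss of data. On the stricter readings, endpoint 3 misses the worst-performing lenses and endpoint 2 can lose a NO; on the softer readings there is no effect.

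A reader might infer a bias of known size. None can be derived: the protocol gives no intolerance rate or expected score change, and its drop-out allowance names no cause. The illustrated 17-point difference on endpoint 2 (83% against 100%) assumes 12 fitted, two intolerant and omitted, and YES for all the others. With 10 analysed, each subject is worth 10 percentage points, so even one replacement would show.

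A correction should be made because it is cheap before data collection and a score not asked for is lost for good. Confidence is medium, since Appendix A may already settle part of it.

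**What to change.** 1. Reword Visit 4 so that awareness and comfort are asked at 45 minutes of wear, or at removal if the lens comes out earlier, with minutes worn recorded. State that the dispense YES/NO is recorded for every subject fitted with the image-guided lens. Bring Appendix A into line if it differs.
2. Amend section 5.0 so that every subject fitted with the image-guided lens is included in the endpoint 2 and 3 summaries, whether or not among the first 10 completers. Report the number who did not reach 45 minutes.

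This changes only what is recorded and analysed, not when a lens is removed.

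**Cost.** One protocol amendment, plus two questions and a time noted at removal, which takes minutes per subject. Scores at early removal reflect shorter wear than the Visit 1 baseline, which follows at least 45 minutes with the habitual lens, so they should be flagged. Results may be less favourable, and more than 10 subjects may be analysed.
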